### **13.0 CRITERIA FOR REMOVAL FROM STUDY**

In accordance with the Declaration of Helsinki, ICH Good Clinical Practice Guidelines, and the US FDA Regulations, a patient has the right to withdraw from the study at any time for any reason without prejudice to his/her future medical care by the physician or at the institution. The Investigator also has the right to withdraw patients from the study (see below). Should a patient (or a patient's legally authorized representative) decide to withdraw, all efforts will be made to complete and report the observations as thoroughly as possible.

A complete final evaluation should be made at the time of the patient's withdrawal, the Study Status Outcome form in the case report form should be completed with an explanation of why the patient is withdrawing, and an attempt should be made to perform a follow-up evaluation.

Patients may be removed from study if one or more of the following events occur:

- Withdrawal of consent by subject
- Occurrence of an AE that precludes further participation
- Subject chooses to take a prohibited treatment, such as use of a different investigational medication or device
- Refusal of the patient to continue treatment observations
- Significant noncompliance on the part of the patient
- Development of another disease (e.g. Adenovirus infection) that requires therapeutic intervention that would interfere with the interpretation of results from the study
- Decision by the Investigator that termination is in the patient's best medical interest
- Lost to follow-up

Patients who received a concomitant antiviral therapy due to toxicity of the current therapy or occurrence of another viral infection will be replaced. Data regarding safety of the CTLs will still be collected for those patients.

### **14.0 BIOSTATISTICS**

A phase 2 trial design will be applied to determine the efficacy and safety of adimlecleucel for the treatment of marrow transplant patients with CMV. The endpoint of this study is complete response or partial response, as defined in Section 12. It is anticipated that accrual will be completed within 3 years.

The study design for HCT recipients aims to detect between response rates of 0.40 and 0.56 in the population. This two-stage design has a target sample size of 69 evaluable patients. If 15 or fewer patients respond in the first 36 patients that are evaluable for outcome assessment, then the trial will be stopped. If at least 16 patients respond, then 33 additional patients will be accrued for therapeutic response assessment. At the conclusion of the trial, if 32 or fewer patient responses are observed, we will conclude that the treatment is not sufficiently active. This design has a power of at least 0.90 for a population CR/PR rate equal to 0.56 using a one-sided test with type 1 error rate of 0.10. To reach 69 evaluable patients, it is anticipated that 81 patients will be recruited.

Based on the limited data in the setting of SOT recipients as well as immune deficient and immune competent individuals, results for these patients will be analyzed separately and will be descriptive.

In order to reduce patient risk, the study design includes early termination in the event of excessive graft versus host disease or solid organ rejection, requiring addition of immunosuppressant therapy to doses above those at the time of enrollment on trial, during the accrual period. The calculation is based on a group sequential design in a single-arm trial with a binary outcome.

Failure type	# of failures needed to stop the study	Failure rate in the population	Probability boundary is crossed
Acute GvHD (grades 3-4)  Or solid organ transplant rejection	3 within the first 15 patients	0.06	0.10
	4 within the first 24 patients  5 within the first 35 patients  6 within 51 patients	0.20	0.90

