## 2.0 OBJECTIVES AND SCIENTIFIC AIMS

### **Primary Objectives:**

1. To assess in a single arm Phase II trial, the therapeutic activity of third party donor derived adimleculeucel for the treatment of clinically overt CMV infection or CMV viremia that is persistent despite 2 weeks of treatment with antiviral agents such as Ganciclovir and /or foscarnet by:
  - a. Partial or Complete decrease in CMV DNA viral load
  - b. Partial or Complete resolution of CMV disease
2. Determine the risk of inducing GvHD or increasing its severity by adoptive transfer of third party donor derived adimleculeucel.

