### **16.2 Data and Safety Monitoring**

The Data and Safety Monitoring Plan utilized for this study must align with the MSK DSM Plan, where applicable.

The Data and Safety Monitoring (DSM) Plans at Memorial Sloan Kettering were approved by the National Cancer Institute in August 2018. The plans address the new policies set forth by the NCI in the document entitled "Policy of the National Cancer Institute for Data and Safety Monitoring of Clinical Trials."

There are several different mechanisms by which clinical studies are monitored for data, safety and quality. At a departmental/PI level there exists procedures for quality control by the research team(s). Institutional processes in place for quality assurance include protocol monitoring, compliance and data verification audits, staff education on clinical research QA and two institutional committees that are responsible for monitoring the activities of our clinical trials programs. The committees: Data and Safety Monitoring Committee (DSMC) for Phase I and II clinical trials, and the Data and Safety Monitoring Board (DSMB) for Phase III clinical trials, report to the Deputy Physician-in-Chief, Clinical Research.

During the protocol development and review process, each protocol will be assessed for its level of risk and degree of monitoring required.

The MSK DSMB monitors phase III trials and the DSMC monitors non-phase III trials. The DSMB/C have oversight over the following trials:

- MSK Investigator Initiated Trials (IITs; MSK as sponsor)
- External studies where MSK is the data coordinating center
- Low risk studies identified as requiring DSMB/C review

The DSMC will initiate review following the enrollment of the first participant/or by the end of the year one if no accruals and will continue for the study lifecycle until there are no participants under active therapy and the protocol has closed to accrual. The DSMB will initiate review once the protocol is open to accrual.

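### The GvHD/rejection stopping table is crossed with probability 0.133 and 0.966, not the stated 0.10 and 0.90, and has no row after patient 51 although 81 HCT recruits are anticipated

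*Combined protocol and SAP*

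**What the plan says.** Section 14.0 (Biostatistics) provides for early termination if GvHD or solid organ rejection is excessive. The text describes the events as "requiring addition of immunosuppressant therapy to doses above those at the time of enrollment on trial, during the accrual period". The calculation is said to rest on a group sequential design for a single arm with a binary outcome.

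The table names the failure as grade 3-4 acute GvHD or solid organ transplant rejection. Its rows are "3 within the first 15 patients", "4 within the first 24 patients", 5 within the first 35, and "6 within 51 patients". The stated probability of crossing is 0.10 if the population failure rate is 0.06, and 0.90 if it is 0.20.

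On sample size, the same section says of the HCT cohort: "To reach 69 evaluable patients, it is anticipated that 81 patients will be recruited". Solid organ recipients and immune deficient or immune competent patients are also enrolled. No number is given for them, and "results for these patients will be analyzed separately and will be descriptive".

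Section 2.0 lists as its second primary objective: "Determine the risk of inducing GvHD or increasing its severity by adoptive transfer of third party donor derived adimleculeucel". Section 16.2 says that Data and Safety Monitoring Committee (DSMC) review "will continue for the study lifecycle until there are no participants under active therapy and the protocol has closed to accrual".

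**The concern.** Two things do not fit. First, the two crossing probabilities are not those of the boundary printed beside them, so a reader is given a false-stop risk that is too low. Second, the rule is said to apply during accrual, yet the last row falls well short of planned accrual.

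This table is the only numeric stopping boundary for a primary safety objective. A failure rate between the two design rates can get past 51 patients without crossing, and from then on no count triggers the rule. The DSMC continues to review the trial but has no printed number to act on.

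Two smaller ambiguities affect how the table would be applied:

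- It does not say whether patients means HCT only or all treated, or evaluable or recruited.
- The text counts events that need added immunosuppression, and the table counts by grade. Whether both conditions must hold is not stated.

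**Working it through.** **Inputs (all from Section 14.0).** Stop at ≥3 failures by patient 15, ≥4 by 24, ≥5 by 35, ≥6 by 51. Failure rates p = 0.06 and 0.20. Stated crossing probabilities 0.10 and 0.90. Planned HCT numbers: 69 evaluable, 81 recruited.

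**Method.** Let f(i, k) be the probability that k failures have occurred among the first i patients and the boundary has not been crossed. Then

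f(i, k) = f(i−1, k)·(1−p) + f(i−1, k−1)·p.

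Whenever k reaches the limit in force at patient i, that probability is moved to the crossed total. The crossing probability is the total after patient 51.

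The first row can be checked by hand at p = 0.06: 1 − [0.94^15 + 15·0.06·0.94^14 + 105·0.06²·0.94^13] = 1 − [0.3953 + 0.3785 + 0.1691] = 0.0571.

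**Cumulative crossing probability by row**

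| Through row | p = 0.06 | p = 0.20 |
|---|---|---|
| 3 in 15 | 0.0571 | 0.6020 |
| 4 in 24 | 0.0794 | 0.7697 |
| 5 in 35 | 0.0996 | 0.8842 |
| 6 in 51 | **0.1334** | **0.9660** |
| Stated in the plan | 0.10 | 0.90 |

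Checking after every patient and checking only at 15, 24, 35 and 51 give identical values, so monitoring frequency does not explain the gap. Simulation agrees (0.1337 and 0.9660 in 400,000 runs).

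**Attempts to reproduce the stated pair**

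| Reading | p = 0.06 | p = 0.20 |
|---|---|---|
| Stop only when the count exceeds the printed number | 0.044 | 0.916 |
| Each limit applied one patient earlier | 0.121 | 0.960 |
| Last row alone | 0.084 | 0.958 |
| First three rows only (to patient 35) | 0.0996 | 0.884 |
| Last row ended at patient 39 | 0.1011 | 0.8958 |
| Last row ended at patient 40 | 0.1022 | 0.9018 |

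No reading of the four printed rows gives 0.10 and 0.90 together. A rule ending near patient 39 or 40 does. That is an observation only; the documents do not say how the figures arose. The failure rates at which the printed rule gives 0.10 and 0.90 are about 5.4% and 16.8%.

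**Chance that 51 patients pass without crossing (1 − crossing probability)**

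| True rate | Crossed by 51 | Not crossed |
|---|---|---|
| 10% | 0.471 | 0.53 |
| 12% | 0.642 | 0.36 |
| 15% | 0.830 | 0.17 |
| 20% | 0.966 | 0.03 |

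**Patients after the last row, if the first efficacy stage is passed**

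- HCT only, evaluable: 69 − 51 = 18 of 69 (26%).
- HCT only, recruited: 81 − 51 = 30 of 81 (37%).
- All treated: the non-HCT number is not given. Assuming 0 to 20 such patients, the range is 30 of 81 (37%) to 101 − 51 = 50 of 101 (50%).

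**The case against.** The arithmetic and the missing rows are not in dispute; the case against concerns how much they matter.

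**Direction of the error.** Both differences make the rule stop more readily: 3.3 points more at 6% and 6.6 points more at 20%. No patient is less protected up to patient 51 than the table claims. This is true and limits the harm. The cost is a higher chance of halting a treatment with an acceptable rate, and the stated figures remain wrong.

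**Coverage.** At 20%, the only excessive rate the plan names, the rule has already crossed with probability 0.966 by patient 51. Rates of 10% or 12% are not called excessive, so passing at those rates does not breach the stated design. Oversight also continues: DSMC review, tracking of grade 3-5 toxicities (Section 11.0), the day-100 GvHD consensus assessment (schedule in Section 10.2.3) and SAE reporting (Section 17.2). This stands as far as it goes. Monitoring does not lapse, but none of these supplies a count that triggers stopping, and the text promises a rule for the whole accrual period.

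**Denominator.** Because organ rejection is a listed failure, an HCT-only count is unlikely, and response-evaluable is a weak safety denominator since Section 13.0 keeps collecting safety data on replaced patients. Both are fair inferences, but the table should say so. If all treated patients count, patient 51 arrives sooner and the uncovered share is larger.

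**Event wording.** Section 11.0 has grade 2-4 GvHD treated with high-dose steroids, and Section 6.1.3 excludes patients needing high-dose steroids at entry. A grade 3-4 case would therefore ordinarily meet both conditions. That makes this a clarification rather than a contradiction.

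**Conclusion.** The concern holds: the table is wrong as written. For the printed boundary the crossing probabilities are 0.133 at 6% (stated 0.10, a third higher) and 0.966 at 20% (stated 0.90, the protective direction). These are exact under independent patients with a common failure rate, stopping when the printed count is reached.

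The rule also ends at patient 51 although it is said to run through accrual. At planned size this leaves 18 of 69 evaluable or 30 of 81 recruited HCT patients with no numeric boundary. The number is larger if non-HCT patients count; the upper figure of 50 of 101 rests on an assumed 20 such patients. The coverage gap matters most for true rates between the two design rates, where passing patient 51 uncrossed is a realistic outcome (0.53 at 10%, 0.17 at 15%).

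The denominator and event definitions are lesser points that need one clear statement each.

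**What to change.** Choose one of two routes for the boundary.

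1. **Keep the printed rows.** Restate the crossing probabilities as 0.13 at 6% and 0.97 at 20%, and say plainly that no numeric rule applies after patient 51.
2. **Extend the boundary** to the full planned number treated and recompute both probabilities.

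Under either route, state which patients the denominator counts (HCT or all treated, evaluable or recruited), and reconcile the event description between text and table.

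Route 1 and the two definitions cost one table and a few sentences, with no extra patients or procedures. Route 2 involves a trade-off. Two examples show that it is feasible; neither is a recommendation:

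| Boundary | Crossed at 6% | Crossed at 15% | Crossed at 20% | By patient 51, at 15% / 20% |
|---|---|---|---|---|
| Printed rows | 0.133 | 0.83 | 0.966 | 0.83 / 0.966 |
| Printed rows plus 7 in 66 and 8 in 81 | 0.189 | 0.95 | 0.997 | 0.83 / 0.966 |
| Re-spaced: 3/12, 4/21, 5/31, 6/42, 7/53, 8/64, 9/76, 10/81 | 0.104 | 0.88 | 0.988 | 0.74 / 0.935 |

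Adding rows raises false stopping to 0.189. Re-spacing keeps it near the intended 0.10 but detects somewhat less by patient 51. If non-HCT patients count, the extension has to run beyond 81, so their planned number must be stated first.

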## 15.0 RESEARCH PARTICIPANT REGISTRATION AND RANDOMIZATION PROCEDURES

### 15.1 Research Participant Registration

Confirm eligibility as defined in the section entitled Inclusion/Exclusion Criteria. Obtain informed consent, by following procedures defined in section entitled Informed Consent Procedures. During the registration process registering individuals will be required to complete a protocol specific Eligibility Checklist. The individual signing the Eligibility Checklist is confirming that the participant is eligible to enroll in the study. Study staff is responsible for ensuring that all institutional requirements necessary to enroll a participant to the study have been completed. See related Clinical Research Policy and Procedure #401 (Protocol Participant Registration).

## **15.2 Randomization**

There is no randomization in this study.

## **16.0 DATA MANAGEMENT ISSUES**

This is a single institution trial and all patients will be treated at Memorial Sloan-Kettering Cancer Center.

A Clinical Research Coordinator (CRC) will be assigned to this study. The responsibilities of the CRC include project compliance, data collection, abstraction and entry, data reporting, regulatory monitoring, problem resolution and prioritization, and coordinate the activities of the protocol study team. The data manager will also monitor laboratory compliance throughout the study. Laboratory data will be tabulated and summarized based on MSKCC normal ranges.

The data collected for this study will be entered into the MSKCC Clinical Research Data Base (CRDB).

### **16.1 Quality Assurance**

Registration reports will be generated by the CRC on a regular basis to monitor patient accruals and completeness of the registration data. Routine data quality reports will be generated to assess missing data and inconsistencies. Accrual rates and extent and accuracy of evaluations and follow-up will be monitored periodically throughout the study period and potential problems will be brought to the attention of the study team for discussion and action.

Random-sample data quality and protocol compliance audits will be conducted by the study team, at a minimum of two times per year, more frequently if indicated.

### **16.2 Data and Safety Monitoring**

The Data and Safety Monitoring Plan utilized for this study must align with the MSK DSM Plan, where applicable.

The Data and Safety Monitoring (DSM) Plans at Memorial Sloan Kettering were approved by the National Cancer Institute in August 2018. The plans address the new policies set forth by the NCI in the document entitled "Policy of the National Cancer Institute for Data and Safety Monitoring of Clinical Trials."

There are several different mechanisms by which clinical studies are monitored for data, safety and quality. At a departmental/PI level there exists procedures for quality control by the research team(s). Institutional processes in place for quality assurance include protocol monitoring, compliance and data verification audits, staff education on clinical research QA and two institutional committees that are responsible for monitoring the activities of our clinical trials programs. The committees: Data and Safety Monitoring Committee (DSMC) for Phase I and II clinical trials, and the Data and Safety Monitoring Board (DSMB) for Phase III clinical trials, report to the Deputy Physician-in-Chief, Clinical Research.

During the protocol development and review process, each protocol will be assessed for its level of risk and degree of monitoring required.

The MSK DSMB monitors phase III trials and the DSMC monitors non-phase III trials. The DSMB/C have oversight over the following trials:

- MSK Investigator Initiated Trials (IITs; MSK as sponsor)
- External studies where MSK is the data coordinating center
- Low risk studies identified as requiring DSMB/C review

The DSMC will initiate review following the enrollment of the first participant/or by the end of the year one if no accruals and will continue for the study lifecycle until there are no participants under active therapy and the protocol has closed to accrual. The DSMB will initiate review once the protocol is open to accrual.

## **17.0 PROTECTION OF HUMAN SUBJECTS**

### **17.1 Privacy**

MSKCC's Privacy Office may allow the use and disclosure of protected health information pursuant to a completed and signed Research Authorization form. The use and disclosure of protected health information will be limited to the individuals described in the Research Authorization form. A Research Authorization form must be completed by the Principal Investigator and approved by the IRB and Privacy Board.

The consent indicates that individualized de identified information collected for the purposes of this study may be shared with other qualified researchers. Only researchers who have received approval from MSK will be allowed to access this information which will not include protected health information, such as the participant's name, except for dates. It is also stated in the Research Authorization that their research data may be shared with others at the time of study publication.

### **17.2 Serious Adverse Event (SAE) Reporting**

All SAEs must be submitted in PIMS. If an SAE requires submission to the HRPP office per IRB SOP RR-408 'Reporting of Serious Adverse Events', the SAE report must be submitted within 5 calendar days of the event. All other SAEs must be submitted within 30 calendar days of the event.

The report should contain the following information:

- The date the adverse event occurred
- The adverse event
- The grade of the event
- Relationship of the adverse event to the treatment(s)
- If the AE was expected
- Detailed text that includes the following
  - An explanation of how the AE was handled

- A description of the participant's condition
- Indication if the participant remains on the study
- If an amendment will need to be made to the protocol and/or consent form
- If the SAE is an Unanticipated Problem

### 17.2.1 Definition of SAE

An adverse event is considered serious if it results in ANY of the following outcomes:

- Death
- A life-threatening adverse event
- An adverse event that results in inpatient hospitalization or prolongation of existing hospitalization
- A persistent or significant incapacity or substantial disruption of the ability to conduct normal life functions
- A congenital anomaly/birth defect
- Important Medical Events (IME) that may not result in death, be life threatening, or require hospitalization may be considered serious when, based upon medical judgment, they may jeopardize the patient or participant and may require medical or surgical intervention to prevent one of the outcomes listed in this definition

Note: Hospital admission for a planned procedure/disease treatment is not considered an SAE.

SAE reporting is required as soon as the participant starts investigational treatment/intervention. SAE reporting is required for 30-days after the participant's last investigational treatment/intervention. Any event that occurs after the 30-day period that is unexpected and at least possibly related to protocol treatment must be reported.

Please note: Any SAE that occurs prior to the start of investigational treatment/intervention and is related to a screening test or procedure (i.e., a screening biopsy) must be reported.

The SAE report should be completed as per above instructions. If appropriate, the report will be forwarded to the FDA by the IND Office

#### Attribution:

- Unrelated: The AE is *clearly NOT related* to the intervention
- Unlikely: The AE is *doubtfully related* to the intervention
- Possible: The AE *may be related* to the intervention
- Probable: The AE is *likely related* to the intervention
- Definite: The AE is *clearly related* to the intervention

### **Expected and Unexpected Event:**

- Expected: Any experience *previously reported* (in nature, severity, or incidence) in the current Investigator's Brochure or general investigational plan
- Unexpected: Any experience *not previously reported* (in nature, severity, or incidence) in the current Investigator's Brochure or general investigational plan

## **18.0 INFORMED CONSENT PROCEDURES**

Before protocol-specified procedures are carried out, consenting professionals will explain full details of the protocol and study procedures as well as the risks involved to participants prior to their inclusion in the study. Participants will also be informed that they are free to withdraw from the study at any time. All participants must sign an IRB/PB-approved consent form indicating their consent to participate. This consent form meets the requirements of the Code of Federal Regulations and the Institutional Review Board/Privacy Board of this Center. The consent form will include the following:

1. The nature and objectives, potential risks and benefits of the intended study.
2. The length of study and the likely follow-up required.
3. Alternatives to the proposed study. (This will include available standard and investigational therapies. In addition, patients will be offered an option of supportive care for therapeutic studies.)
4. The name of the investigator(s) responsible for the protocol.
5. The right of the participant to accept or refuse study interventions/interactions and to withdraw from participation at any time.

Before any protocol-specific procedures can be carried out, the consenting professional will fully explain the aspects of patient privacy concerning research specific information. In addition to signing the IRB Informed Consent, all patients must agree to the Research Authorization component of the informed consent form.

Each participant and consenting professional will sign the consent form. The participant must receive a copy of the signed informed consent form.

